4.4 Exclusion Criteria

1. Women who are pregnant or breast-feeding.
2. Clinical suspicion that etiology of illness is primarily bacterial in origin.
3. Prior treatment with antivirals (e.g. oseltamivir) for the current illness for more than 24 hours.
4. Subjects unable to take enteral medications (adults must tolerate tablets by mouth as they cannot be crushed, children must be able to swallow pediatric suspension or receive drug by nasogastric tube).
5. Prior treatment with any investigational drug therapy within 30 days prior to screening.
6. Known sensitivity to NTZ or any of the excipients comprising the NTZ tablets.
7. Prior NTZ use within 1 week.
8. Self-reported history of impaired renal function (no blood or urine kidney function laboratory testing will be done prior to enrollment, but intent is to exclude disease severe enough to cause estimated $\text{CrCl} < 30 \text{ mL/min}$).
9. Self-reported history of liver disease (no blood laboratory testing will be done prior to enrollment, but intent is to exclude disease severe enough to cause cirrhosis or total bilirubin $> 1.5 \times \text{ULN}$, $\text{AST}/\text{ALT} > 3 \times \text{ULN}$, based on labs obtained previously for clinical diagnosis).

10. Presence of any pre-existing medical condition not listed above that, in the opinion of the investigator, would place the subject at an unreasonably increased risk through participation in this study.
11. Subjects who, in the judgment of the investigator, will be unlikely to comply with the requirements of this protocol.
12. The onset of respiratory symptoms occurs after hospitalization (to exclude nosocomial infections).
13. Hospitalized for any reason for greater than 60 hours prior to enrollment.
14. Participants previously enrolled in this study.
15. Known chronic respiratory infection (e.g., tuberculosis, atypical mycobacterial infections).

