6.2.8 Hospital Discharge Evaluation

Near the time of hospital discharge, data pertaining to the hospitalization will be collected. If subjects are still hospitalized after Day 28, they will be followed through hospital discharge.

A discharge source document and CRF should be completed by reviewing the medical chart within 4 days of discharge (if subjects are hospitalized for over 28 days, this evaluation should be done within 10 days of the day of discharge). This will document:

- Date and hour of discharge
- Date of death (if applicable)
- Oxygen use during hospitalization
- Dates of admission to ICU and discharge from ICU (if applicable)
- Dates of intubation/extubation (if applicable)

- Antibiotic/antiviral use during hospitalization (number and duration)

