## 12. Secondary Endpoint (ITT and ITT age subgroups)

For secondary endpoints that test proportion:

- Deaths are always counted as worst case (i.e. deaths are counted as being hospitalized through Day 28).
- Missing data is analyzed in two ways:
  - Missing data is excluded after date of last follow-up. i.e. any analysis after the date of last follow up will exclude the missing subject from the denominator. This represents the “best case” for the missing data.
  - Missing data is assigned the worst case. i.e. for hospitalization, this missing data would be assumed to be hospitalized through Day 28. This represents the “worst case” scenario for the missing data.

For secondary endpoints that are time to events, the Fay-Shaw method accounts for deaths and missing data. In cases where the Fay-Shaw method is not appropriate, the Log-Rank p-value will be reported.

- Percent hospitalized at Study Day 3, 7, 14 and 28 [14.2.3.2.x]
  - Table N (%) hospitalized at Study Day 3, 7, 14 and 28 and test of proportions
  - Figure of proportions at each time point
- Duration of clinical symptoms [14.2.4.1.x]  
Subjects with 0-1 on all symptoms on Day 0 are considered to have a time of 0 hours.
  - Table: time (in hours) from symptom onset to symptom free (symptom free is 0-1 on all symptoms that last at least 2 days), noting min, 25%tile, 50%tile, 75%tile
    - P-value obtained using Shaw-Fay method (here only treat deaths as worst rank and missing as censored)
  - Figure using Kaplan-Meier plot.
- Duration of fever- defined as temperature  $\geq 38.0$  C [14.2.4.2.x]
  - Table: v with min, 25%tile, 50%tile, 75%tile, max.
    - P-value obtained using Shaw-Fay method (here only treat deaths as worst rank and missing as censored)

- Figure using Kaplan-Meier plot.
- Use of supplemental oxygen (or increase greater than baseline oxygen requirement) [14.2.5.1.x]
  - Resolution is defined as off oxygen. Subjects without stop date will be censored at 28 days. A time of 00:00 will be imputed for subjects with a stop date but missing stop time.
  - Table N (%) of use of oxygen (Y/N) at any point during the study, and at each time point
    - P-value obtained using test of proportions
  - Figure of proportions at each time point
  - Table duration of oxygenation: defined as time of oxygen first administered, to time off oxygen (in hours) noting min, 25%tile, 50%tile, 75%tile, max [14.2.5.2.x]
    - Table includes all subjects – where subjects not requiring oxygen have 0 hours.

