    - P-value obtained using Shaw-Fay method (here only treat deaths as worst rank and missing as censored)
  - Table duration of oxygenation: defined as time of oxygen first administered, to time off oxygen (in hours) noting min, 25%tile, 50%tile, 75%tile, max [14.2.5.3.x]
    - Table is restricted to those requiring oxygen at any point during the study.
    - P-value obtained using Shaw-Fay method (here only treat deaths as worst rank and missing as censored)
  - Figure using Kaplan-Meier plot
    - Figure includes all subjects – where subjects not requiring oxygen have 0 hours.
    - Figure is repeated, but restricted to those requiring oxygen at any point during the study.
- Admission to ICU
  - Table N (%) of requiring ICU (Y/N) at any point during the study, and at each time point [14.2.6.1.x]
    - P-value obtained using test of proportions
  - Figure of proportions at each time point
  - Table duration of ICU: defined as time subject admitted to ICU, to time discharged from ICU (in hours) noting min, 25%tile, 50%tile, 75%tile, max [14.2.6.2.x]
    - Table includes all subjects – where subjects not requiring ICU have 0 hours.
    - P-value obtained using Shaw-Fay method (here only treat deaths as worst rank and missing as censored)
  - Table duration of ICU: defined as time subject admitted to ICU, to time discharged from ICU (in hours) noting min, 25%tile, 50%tile, 75%tile, max [14.2.6.3.x]
    - Table is restricted to those requiring ICU at any point during the study.
    - P-value obtained using Shaw-Fay method (here only treat deaths as worst rank and missing as censored)
  - Figure using Kaplan-Meier plot
    - Figure includes all subjects – where subjects not requiring ICU have 0 hours.
    - Figure is repeated, but restricted to those requiring ICU at any point during the study
- Intubation/mechanical ventilation
  - Table N (%) of requiring mechanical ventilation (Y/N) at any point during the study, and at each time point [14.2.7.1]

- P-value obtained using test of proportions
- Figure of proportions at each time point
- Table duration of mechanical ventilation: defined as time subject placed on mechanical ventilation, to time extubated (removed from mechanical ventilation) noting min, 25%tile, 50%tile, 75%tile, max [14.2.7.2.x]
  - Table includes all subjects – where subjects not requiring mechanical ventilation have 0 hours.
  - P-value obtained using Shaw-Fay method (here only treat deaths as worst rank and missing as censored)

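### Oxygen, ICU and ventilation durations include hours before randomisation for subjects already on support at Day 0, which dilutes these secondary comparisons without biasing them

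*SAP*

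**What the plan says.** SAP section 12 defines three support durations:

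- Oxygen: "defined as time of oxygen first administered, to time off oxygen (in hours".
- ICU: "defined as time subject admitted to ICU, to time discharged from ICU (in hours".
- Mechanical ventilation: "defined as time subject placed on mechanical ventilation, to time extubated (removed from mechanical ventilation".

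Each is tabulated twice, once for all subjects with non-users at 0 hours, and once for users only. For oxygen, the second "Table is restricted to those requiring oxygen at any point during the study". Each table carries a between-arm test: "P-value obtained using Shaw-Fay method (here only treat deaths as worst rank and missing as censored". For oxygen the SAP adds: "Subjects without stop date will be censored at 28 days". It does not say from when the 28 days run. Neither document moves the start to randomisation or first dose for a subject who is already on support.

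Such subjects are expected. SAP section 3 tabulates oxygen requirement, ICU requirement, respiratory failure with ventilation, and chronic oxygen use at baseline. Protocol 4.4 excludes subjects "Hospitalized for any reason for greater than 60 hours prior to enrollment", so shorter prior stays are allowed. Protocol 6.2.8 collects "Oxygen use during hospitalization", which is not limited to time on study.

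Time origins differ elsewhere in the SAP. Death is timed from randomisation (section 7), global assessment from enrolment and symptom duration from symptom onset (both section 12).

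**The concern.** For a subject on oxygen or in the ICU at Day 0, the measured duration is the sum of two parts: hours before randomisation, which treatment cannot affect, and hours after it, which it might. The rank test sees only the sum. Variation in the first part blurs the ranking on the second, and two subjects can be ordered the opposite way from their course on treatment. What is at stake is sensitivity in the six duration tables, and a plain description of how much support was needed once treatment began.

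**Working it through.** **Figures in the plan.** None is given for these durations, and Protocol 9.2 says secondary endpoints may not be adequately powered. Two figures there are useful as anchors. The planned 290 subjects give 290/2 = 145 per arm. The hoped-for effect on hospital stay is 1.25/7.7 = 16.2%, matching the protocol's 16% (its printed formula shows 1 day in the numerator, but 1/7.7 would be 13%). A 16% shorter course is a ratio of 0.84.

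**Can the order of two subjects reverse?** Subjects A and B reverse when (pre A − pre B) exceeds (post B − post A) and both differences are positive.

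- A: 48 h before + 48 h after = 96 h.
- B: 6 h before + 72 h after = 78 h.

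A needs 24 h less oxygen after randomisation but 42 h more before it, so A ranks worse. The 60-hour limit permits this.

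**How often?** Assume all subjects are on support at Day 0, prior hours are uniform on 0-60, and later hours are log-normal with log SD 0.7. The share of reversed pairs is 25.5%, 16.1%, 9.0% and 5.3% at later medians of 24, 48, 96 and 168 h. With prior hours capped at 24 it runs from 13.5% down to 2.2%.

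**Power for oxygen.** None of the following inputs is in the documents except the 145 per arm. Assume 65% are on oxygen at Day 0 and 5% of the rest start later, so users are 0.65 + 0.35 × 0.05 = 67%. Non-users have 0 h. Hours after randomisation are log-normal with median 72 h times the treatment ratio and log SD 0.9. Prior hours are uniform on 0-60 or 0-24. A two-sided 0.05 Mann-Whitney test stands in for Shaw-Fay, with no deaths or censoring.

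| Shorter course on NTZ | Prior oxygen | Subjects | Power, clock from randomisation | Power, SAP clock | Loss (points) |
|---|---|---|---|---|---|
| 16% | 0-60 h | all | 10.7% | 10.0% | 0.7 |
| 16% | 0-24 h | all | 11.3% | 10.9% | 0.4 |
| 25% | 0-60 h | all | 22% | 20% | 2 |
| 25% | 0-60 h | users | 58.1% | 52.9% | 5.2 |
| 35% | 0-60 h | all | 43.8% | 38.2% | 5.6 |
| 35% | 0-60 h | users | 89.6% | 85.2% | 4.4 |
| 40% | 0-60 h | all | 57.6% | 50.2% | 7.4 |
| 40% | 0-60 h | users | 97.5% | 93.7% | 3.8 |
| 35% | 0-24 h | all | 42.6% | 40.8% | 1.8 |
| 40% | 0-24 h | all | 56.2% | 54.7% | 1.5 |

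For users only at 16%, the loss is about 3 points or less. With 2000 runs, the standard error of a single power figure is at most √(0.5 × 0.5/2000) = 1.1 points, so differences of a point between rows mean little.

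**Stress case.** If everyone were on support at Day 0 (73 per arm, log SD 0.7, 25% shorter course, 0-60 h prior), power would fall from about 66-68% to 33%, 51% or 63% at later medians of 24, 48 or 96 h. The loss grows as prior hours become long relative to later ones.

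**Type I error.** With no treatment effect, the SAP clock rejects in 4.4-5.7% of simulated trials under the stress-case model and 5.0-5.5% under the main model.

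**The case against.** The strongest reply is that this is a small matter in unpowered secondary tables. Most of that stands:

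- **Effect size.** The larger losses need a 35-40% shorter course. At the protocol's own 16%, the all-subject comparison has about 10% power on either clock.
- **Prior hours.** Sixty hours caps hospital stay, not oxygen time. Protocol 6.2.1 asks for early enrolment and a first dose within 24 hours, so 0-60 h is close to a ceiling.
- **Whole-episode duration is a legitimate quantity.** Symptom duration is also timed from before randomisation. The planned comparisons of the proportion on support contain no prior hours at all.
- **Ventilation.** Protocol 4.4 requires adults to swallow uncrushed tablets, so few can be ventilated at entry.

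One reply does not stand. First administration could be read as first within the study, but the SAP does not say so. The phrase about use at any point during the study decides who enters the restricted table, not when the clock starts.

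A reader might go further and infer that the comparison is biased, or that reversed pairs could produce a false positive. The documents do not support this: allocation is random and blinded, so prior hours have the same distribution in both arms. A reader might also take the stress case as the expected loss. The documents do not give its inputs: everyone on support at entry, and a 25% effect on these durations.

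**Conclusion.** The point holds as a matter of definition and efficiency. As written, the oxygen, ICU and ventilation durations of subjects on support at Day 0 include hours that treatment cannot change. The result is noise, a diluted effect and reported hours that overstate support after treatment starts. There is no systematic bias, type I error is unaffected, and the primary endpoint and sample size are untouched.

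Under the main assumed inputs, the power loss for oxygen is about 0-1 point (all subjects) or up to 3 points (users only) for a 16% shorter course. It is about 5-7 points (all subjects) or 3-5 points (users only) for a 35-40% shorter course with 0-60 h of prior oxygen, and about 1-2 points or less with 0-24 h. These sizes rest on an assumed share of Day 0 users and assumed duration distributions. ICU was not simulated; the same mechanism applies to it, but its size depends on how many subjects enter from the ICU. This is an inexpensive improvement worth making before unblinding, not a defect that threatens the trial's conclusions.

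**What to change.** In SAP section 12, define each duration as hours of support after randomisation:

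- **Start:** the later of randomisation and start of support. Anyone off support before randomisation gets 0 hours; without this clause the rule would give them a negative duration.
- **If no randomisation clock time is recorded,** start from the first-dose time. The protocol defines Day 0 only as a day. Every subject in the ITT population has a first dose by definition.
- **End:** count through Day 28 from the same origin, and say so in the oxygen censoring rule.
- **Chronic oxygen users:** count only use above the baseline requirement, as the endpoint heading implies. State what baseline means here, because SAP section 3 defines it as the last observation before study drug, which need not be the chronic requirement.
- **Consistency:** use this definition for the tables, the Shaw-Fay p-values and the Kaplan-Meier plots.
- **Hours before randomisation:** report them as a baseline characteristic.

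The cost is a slightly longer derivation. Times of day are needed for ICU and intubation, where Protocol 6.2.8 lists only dates, although the SAP's ICU table already asks for hours. The tables would no longer describe the whole support episode; the baseline summary of earlier hours partly replaces that.

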2.2 Secondary Objectives

1. Evaluate the clinical efficacy of NTZ + SOC vs. PCB + SOC with regards to:
 - Percent hospitalized at Study Day 3, 7, 14 and 28
 - Death by Study Day 28
 - Duration of clinical symptoms (defined in Section 7.3.1.2)
 - Duration of fever
 - Use of supplemental oxygen (or increase greater than baseline oxygen requirement)
 - Admission to ICU
 - Intubation/mechanical ventilation
 - Proportion of subjects who develop complications including pneumonia, respiratory failure requiring mechanical ventilation, acute respiratory distress syndrome (ARDS), sepsis, or bronchiolitis.
 - Time to resumption of normal activity
 - Antibiotic/antiviral use during hospitalization
 - Systemic corticosteroid use during hospitalization
 - Re-hospitalization within 28 days
2. Evaluate the virologic efficacy of NTZ + SOC vs. PCB + SOC with regards to:
 - Percent cessation of viral shedding at Study Day 3
3. Evaluate the safety and tolerability of NTZ assessed by:
 - Cumulative incidence and severity of AEs
 - Cumulative incidence of SAEs
 - Cumulative incidence of laboratory abnormalities on Study Days 3, 7 and 28

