3.6.2 Secondary Endpoints

Clinical Endpoints:

- Hospitalization on Study Days 3, 7, 14, and 28
- Date and time of hospital discharge
- Date of death, if applicable
- Clinical symptoms (measured daily through Study Day 14 and then again on Study Day 28)
- Temperature (measured daily through Study Day 14 and then again on Study Day 28)
- Oxygen use
- Date of admission to ICU and discharge from ICU, if applicable
- Date of intubation/extubation, if applicable
- Presence of complications during study (pneumonia, respiratory failure requiring mechanical ventilation, ARDS, sepsis, or bronchiolitis)

- Global assessment (measured daily through Study Day 14 and then again on Study Day 28) (defined in Section 7.3.1.3)
- Antibiotic/antiviral use during hospitalization (number and duration)
- Re-hospitalization within 28 days
- Use of systemic corticosteroids

Virologic Endpoints:

- Presence of virus on nasopharyngeal (NP) swab (or aspirate) on Study Day 3 (same virus as Day 0)

Safety Endpoints:

- AEs
- SAEs
- Chemistry and hematologic laboratory assessments on Study Days 3, 7 and 28

4 STUDY POPULATION**4.1 Rationale for Research Subject Selection**

The inclusion criteria define those subjects with SARI. In an ongoing LaRed study, similar ILI criteria have been successful in identifying a population whose respiratory illness is caused by a virus 70% of the time.

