7.2 Viral Diagnostics

The NP swab on Days 0 and 3 will be tested by a central lab using a multiplex PCR for 22 respiratory pathogens and influenza types. The platform, Respifinder®, will be used according to manufacturer instructions. This multiplex PCR test can detect and differentiate 18 viruses (Coronavirus NL63, OC43, 229E, HKU1, Human metapneumovirus, Influenza A, Influenza A H1N1v, Influenza B, Parainfluenza 1 to 4, Respiratory syncytial virus (RSV) A and B, Rhinovirus/Enterovirus, Adenovirus, Bocavirus) as well as 4 bacteria (*Bordetella pertussis*, *Chlamydophila pneumoniae*, *Legionella pneumophila*, *Mycoplasma pneumoniae*).

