#### Virologic Endpoints:

- Presence of virus on nasopharyngeal (NP) swab (or aspirate) at Study Day 3 (same virus as Day 0)

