- Evaluate the virologic efficacy of NTZ + SOC vs. PCB + SOC with regards to:  
Restricted to those with virus detectable on Day 0
  - Table N (%) of subjects that had any virus detectable on Day 0, and no longer had any virus detectable on Day 3 [14.2.11]
    - If more than one virus was present on Day 0, both viruses must be cleared to be considered as no detectable virus. If Day 3 has a virus that was not detected on Day 0 (day 0 had virus A and Day 3 virus B), this is not considered as having no detectable virus.
    - P-value obtained using test of proportions
  - Table N (%) of subjects that had virus detectable on Day 0, and had a different virus detectable on Day 3.

## Appendix 1

The primary endpoint is time to hospital discharge or death within 28 days. The primary analysis will follow the intent to treat principal where all patients randomized will be used in the analysis and analyzed according to treatment assignment. Observations will be censored at 28 days if discharge or death does not occur before 28 days.

The Shaw-Fay methodology uses ranks to form the test statistic. The following ranking system will be followed if no loss to follow up occurs. Patients who die will be given worse ranks than those who are alive. Among those who die, early deaths receive worse ranks than those who are alive and among those alive the order of ranking from worst to best is no discharge, late, than early discharge. Table 1 gives an example of rankings for an invented data set.

Table 1. Example of rankings for invented data set. C indicates censored at day 28 or censored due to death. Larger ranks are worse than smaller ranks.

Person	Day of discharge	Day of Death	Rank
1	C	5	8
2	C	10	7
3	3	15	6
4	C	C	5
5	15	C	4
6	5	C	3

7	2	C	1.5
8	2	C	1.5

The test statistics is the sum of the ranks for patients in the Nitazoxanide group. Treatment labels will be permuted to calculate the probability of obtaining a test statistic as extreme as the observed sum of the ranks of the experimental group.

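### SAP section 12 scores a patient who cleared every Day 0 virus but has a new virus on Day 3 as not cleared, so the only tested virologic proportion is not the stated endpoint

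*SAP*

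**What the plan says.** - **Protocol 2.2** gives the virologic objective as "Percent cessation of viral shedding at Study Day 3". It does not say which virus.
- **Protocol 3.6.2** gives the endpoint: "Presence of virus on nasopharyngeal (NP) swab (or aspirate) on Study Day 3 (same virus as Day 0"). The protocol summary has the same restriction to the Day 0 virus.
- **SAP, Virologic Endpoints**, repeats it: "Presence of virus on nasopharyngeal (NP) swab (or aspirate) at Study Day 3 (same virus as Day 0").
- **SAP section 12** sets the analysis population ("Restricted to those with virus detectable on Day 0") and counts as successes those who "no longer had any virus detectable on Day 3". If several viruses were present on Day 0, all must clear. If Day 3 shows a virus that was absent on Day 0, "this is not considered as having no detectable virus". This proportion gets a P-value from a test of proportions.
- **SAP section 12** adds a second output, with no P-value listed: "Table N (%) of subjects that had virus detectable on Day 0, and had a different virus detectable on Day 3".
- **Protocol 7.2** says of the assay used on Days 0 and 3: "This multiplex PCR test can detect and differentiate 18 viruses".

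**The concern.** The restriction to the Day 0 virus appears in the protocol summary, in protocol 3.6.2 and in the SAP's endpoint list, and the analysis section then departs from it without giving a reason. The SAP therefore conflicts both with the protocol and with itself, and no analysis of the stated endpoint is planned, even as a sensitivity analysis.

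Virologic efficacy is a numbered secondary objective, and this is the only virologic proportion that gets a P-value. Under the section 12 rule, that P-value mixes two events: clearance of the infection present at randomization, and detection of a different virus about three days later. A reader of the results would take the figure for the first event alone.

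**Working it through.** **1. The definitions side by side.** For a patient with virus A on Day 0:

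| Day 3 result | Stated endpoint (A still present?) | SAP section 12 |
|---|---|---|
| none | cleared | cleared |
| A | not cleared | not cleared |
| A and B | not cleared | not cleared |
| B only | **cleared** | **not cleared** |

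The definitions disagree in the last row only, and always in the same direction: a clearer becomes a failure.

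**2. Can the two planned tables be combined to recover the endpoint?** Among Day 0 virus-positive patients in an arm, let a = cleared with no new virus, b = cleared with a new virus, c = not cleared with no new virus, d = not cleared with a new virus. The first table reports a. The second, as worded, reports b + d. The stated endpoint needs a + b. Since b and d are not separated, a + b is known only to lie between a and a + b + d.

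**3. Effect on the comparison.** The documents state no power, sample size or clearance rate for this endpoint, so there is no figure of the plan to reproduce. Let p be true clearance of the Day 0 virus and q the share of clearers with a new virus on Day 3. The SAP rule observes p × (1 − q).

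If q is equal in both arms, the difference is (p_NTZ − p_placebo) × (1 − q).

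Inputs:
- 290 randomized 1:1 (protocol 3.4).
- Virus-positive share from protocol Table 2: (1376 − 551 negative − 7 *B. pertussis* − 20 *M. pneumoniae*) / 1376 = 798/1376 = 58%. Then 290 × 0.58 / 2 ≈ 84 per arm.
- Assumed, not in the documents: clearance 45% on placebo and 65% on NTZ, all values of q, two-sided alpha 0.05 for this test, and a Day 3 result for every virus-positive patient.

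Power = Φ[(difference − 1.96 × SE0) / SE1], with SE0 from the pooled proportion and SE1 from the two separate proportions. At q = 0, SE0 = √(2 × 0.55 × 0.45 / 84) = 0.0768 and SE1 = √((0.45 × 0.55 + 0.65 × 0.35) / 84) = 0.0752. Power is Φ[(0.20 − 0.1505) / 0.0752] = Φ(0.66) = 74.5%.

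| q, both arms | Observed rates | Difference (points) | Power |
|---|---|---|---|
| 0 | 45.0% vs 65.0% | 20.0 | 74.5% |
| 2% | 44.1% vs 63.7% | 19.6 | 72.6% |
| 5% | 42.8% vs 61.8% | 19.0 | 69.7% |
| 10% | 40.5% vs 58.5% | 18.0 | 64.8% |
| 20% | 36.0% vs 52.0% | 16.0 | 55.2% |

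**4. Unequal new-virus rates.** Same clearance rates and numbers:
- q = 10% placebo, 5% NTZ: 0.65 × 0.95 − 0.45 × 0.90 = 0.6175 − 0.405 = 21.3 points, power 79.2%.
- q = 5% placebo, 10% NTZ: 0.65 × 0.90 − 0.45 × 0.95 = 0.585 − 0.4275 = 15.8 points, power 53.3%.

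The first exceeds the true 20 points and the second falls short of it.

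**5. Sensitivity to the assumptions.** With a 60% virus-positive share (290 × 0.60 / 2 = 87 per arm) and clearance of 30% vs 50%, power is 77.3% at q = 0, 73.7% at 5%, 69.9% at 10% and 62.1% at 20%. With a 70% share (101 per arm) and the same clearance, it is 83.2% at q = 0, 76.4% at 10% and 68.6% at 20%.

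**The case against.** The section 12 rule is explicit, pre-specified and illustrated with an example, so it was probably intended. The objective names no particular virus and, read alone, fits an any-virus definition. The second table shows that the authors had patients with a new virus in mind. An any-virus definition is a defensible choice. All of this stands, but it does not remove the conflict: the endpoint text, which the SAP itself repeats, is more specific than the objective, and the second table cannot restore the missing proportion.

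A reader might infer that the rule necessarily dilutes the treatment effect. The documents do not support that. Dilution requires new detections to be equally frequent in both arms, and nothing in either document says they are. Protocol 1.2.2 attributes the breadth of antiviral activity to a cell-mediated effect, so NTZ could also affect newly acquired viruses; the same section says rhinovirus is not thought to be inhibited. Step 4 shows that the observed difference can rise as well as fall.

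The size is also uncertain. At a 2% new-virus rate, the power loss in step 3 is about 2 points. The 58% share treats all 150 mixed cases in Table 2 as viral and comes from patients aged 2 years and over, whereas the trial enrolls from 12 months. The documents elsewhere give about 60% (protocol summary) and 70% (protocol 4.1). Protocol 9.2 already warns that secondary endpoints may lack power.

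Finally, matching the same virus needs a rule that neither document supplies. The panel reports Influenza A and H1N1v as separate targets and combines rhinovirus with enterovirus. This affects the remedy and is taken up there.

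**Conclusion.** The point holds as a definitional conflict and needs no assumption: the variable tested in SAP section 12 is not the endpoint stated in the protocol and in the SAP's own list, and the planned outputs do not allow the stated endpoint to be reported.

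The resulting bias is of unknown size, and its direction is known only under equal new-virus rates, when the difference shrinks by (1 − q). On the assumed 84 per arm and 45% vs 65% clearance, equal rates between 2% and 20% would cost roughly 2 to 19 power points. These figures are illustrative, because the documents contain neither a clearance rate nor a new-virus rate. The primary endpoint and the sample size are unaffected. The change should be made before unblinding, but it does not threaten the trial's main conclusion.

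**What to change.** In SAP section 12:
1. Define clearance as none of the viruses detected on Day 0 being detected on Day 3, with all of them required to clear in mixed infections. Apply the test of proportions to this variable.
2. State the level at which panel targets are matched, for example whether Influenza A followed by H1N1v counts as the same virus, and that a persisting and a new infection within the combined Rhinovirus/Enterovirus target cannot be told apart.
3. Keep the different-virus table, split by whether the Day 0 virus cleared.
4. Show the any-virus definition as a sensitivity analysis.

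If the sponsor prefers the any-virus definition as the main one, the conflict can instead be removed by amending the endpoint wording in the protocol summary, protocol 3.6.2 and the SAP endpoint list, with a reason, before unblinding.

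The cost is a short SAP revision, a matching rule, one changed derivation and a few extra table rows. The assay already reports the targets separately on both days, so no new samples or tests are needed.
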